3.2 Sample Size

One hundred eighty-eight PFS events are required to have at least 90% power to demonstrate superiority at an alternative HR of 0.6 (arm 1 vs arm 2), using a log rank test at 1-sided overall significance level of 0.025. CCI

CCI

CCI. With 450 subjects randomized (300 in arm 1 vs 150 in arm 2), it is anticipated that 188 events will be accrued at approximately 27 months after the first subject is

randomized assuming events follow an exponential distribution. CCI [REDACTED]

[REDACTED]

[REDACTED]

[REDACTED]

[REDACTED]

[REDACTED]

[REDACTED]

[REDACTED] The description of sample size calculation for log-rank test factoring in accrual and dropout can be found in Lachin and Foulkes, 1986; Lakatos, 1988; and Chow et al, 2003. The actual timing of primary analysis will be determined by actual enrollment rate, dropout rate, and PFS event rate; hence, it is subject to change as these factors may vary in the study. The minimum detectable PFS HR that will achieve statistical significance is approximately 0.738 (corresponding to about 36% improvement in PFS) at the primary analysis. Amgen may choose to increase sample size upon observation of slower than expected PFS event rate.

CCI [REDACTED]

The sample size calculation was performed using East[®] software (Version 6.3 or above).

4. Covariates and Subgroups

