It will be calculated as the planned cumulative dose of **daratumumab** in mg/kg divided by the planned number of weeks for the treatment per protocol based on the corresponding cycle and day of the last **daratumumab** infusion. Per protocol, one cycle is 28 days (4 weeks), so the planned number of treatment weeks will be calculated as $4 \times (c-1) + j$, where c is the cycle in which the last daratumumab infusion is given and j =1 if the last daratumumab infusion is given on day 1 or 2 within the last cycle, j=2 if the last infusion is given on day 8, j=3 if the last infusion is given on day 15, j=4 if the last infusion is given on day 22. The planned cumulative dose of **daratumumab** is the summation of planned **daratumumab** dose (mg/m²) per week as : [8x2, 16x1, 16x1, 16x1] in cycle 1; [16x1, 16x1, 16x1, 16x1] in cycle 2; [16x1, 0, 16x1, 0] in cycle 3-6; and [16x1, 0, 0, 0] in all other cycles.

Study Day 1

Study Day 1 is the first day that the protocol-specified investigational products are administered to the subject.

Time to Complete Response

Time to complete response will be calculated only for the subjects who achieve a best overall response of CR or better, ie, sCR or CR. It will be calculated in months from randomization date to the earliest date of response of CR or better is first achieved and subsequently confirmed:

$$\text{Time to Complete Response} = (\text{response start date} - \text{randomization date} + 1) / 30.4$$

Time to Next Treatment

Time to next treatment is defined as the time (in months) from randomization to the initiation of subsequent non-protocol anti-cancer treatment for multiple myeloma.

Time to Progression (TTP)

TTP is defined as the time (in months) from randomization to documented disease progression.

Time to Response

Time to response will be calculated only for subjects who achieve a best overall response of PR or better, ie, sCR, CR, VGPR, or PR. It will be calculated in months from randomization date to the earliest date a response of PR or better is first achieved and subsequently confirmed:

$$\text{Time to Response} = (\text{response start date} - \text{randomization date} + 1) / 30.4$$

Treatment-emergent Adverse Event

Treatment-emergent adverse events (TEAE) are events with an onset after the administration of the first dose of any **study treatment** and within **the end of study or 30 days of the last dose of any study treatment, whichever occurs earlier**.

6. Analysis Sets

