9.5.1 Analyses of Primary Efficacy Endpoint(s)

The distribution of PFS time including median and quartiles will be summarized descriptively using the Kaplan-Meier method. The corresponding 95% confidence intervals for the median and quartiles will be constructed using the method of [Klein and Moeschberger \(1997\)](#) with log-log transformation. PFS rates at selected landmark time points will be provided and the corresponding 95% confidence intervals will be calculated using the method of [Kalbfleisch and Prentice \(1980\)](#). The duration of the follow-up for PFS will be estimated by reverse Kaplan-Meier method ([Schemper and Smith 1996](#)).

The inferential comparison between treatment groups will use the log-rank test stratified by the randomization stratification factors per IXRS at level of 0.025 (1-sided). The HR

and its 95% CI will be estimated using a Cox proportional hazards model stratified by the same randomization stratification factors.

The primary endpoint of PFS will be analyzed within each of the subgroups listed in [section 4](#). Specifically, to determine whether the treatment effect is consistent across subgroups, the estimate of the hazard ratios (with 95% CI) for PFS between the treatment groups will be provided. Additionally, a treatment-by-subgroup interaction test **may** be provided using a Cox proportional hazards model stratified by the stratification factors.

Piecewise Cox models may be explored given evidence of non-proportional hazards (Collett, 2003). This model will allow estimation of an overall weighted hazard ratio (weights equal to fraction of total events in each interval (Lu & Pajak, 2000)) as well as within interval treatment hazard ratio. Additional analysis may be performed to explore potential sources for non-proportionality by considering baseline prognostic factors and other potential confounding factors.

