Duration of response (DOR) is defined as the time (in months) from first evidence of PR or better per IMWG-URC to the earlier of disease progression or death due to any cause for subjects with a best response of PR or better. For those who are alive and have not experienced disease progression at the time of data cutoff for analysis, duration of response will be right-censored based on the censoring conventions defined previously for PFS (refer to [Table 1](#)). The distribution of DOR, including the median and quartiles and their corresponding 95% CIs, will be characterized using the Kaplan-Meier method based on the subjects who achieve a best response of PR or better. No inferential comparison between treatment arms will be made for duration of response.

Time to next treatment is defined as the time (in months) from randomization to the initiation of subsequent non-protocol anti-cancer treatment for multiple myeloma. Time to next treatment for subjects who do not start the subsequent treatment for multiple myeloma will be censored at the date when the subject's information is last available. Time to next treatment will be summarized descriptively using the Kaplan-Meier method. This analysis will be based on the ITT population.

Time to progression (TTP) is defined as the time (in months) from randomization to documented disease progression. Analysis of TTP will be the same as PFS (see Section 8.4.1.1) except that death will be treated as a censoring event for TTP and will use similar methods as those for the primary PFS analysis based on the ITT population.

For descriptive purposes, time to overall response (defined as the time [in months] from randomization to the earliest of sCR, CR, VGPR, or PR per IMWG-URC) will be summarized using the descriptive statistics for a continuous variable by treatment group for those who achieve a best response of sCR, CR, VGPR, or PR.

The rate of sustained MRD[-]CR (defined as the proportion of subjects that maintain MRD[-]CR for 12 months or more after achieving MRD[-]CR status), the CRR rate (defined as the proportion of best overall response of sCR or CR), and the MRD[-] rate at 12-month will be compared between treatment groups using the similar method for ORR/MRD[-]CR analysis.

The inferential analysis of the endpoint of QLQ-C30 Global Health Status/QOL scale is described in [section 9.7.2](#).

CCI

CCI

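### Time to progression and time to next treatment censor deaths and are summarised by Kaplan-Meier, so within each arm the curves overstate how many subjects have the event and the medians fall too early

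*SAP*

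**What the plan says.** For TTP, SAP Section 9.5.2 states that "Analysis of TTP will be the same as PFS", with one change: "death will be treated as a censoring event for TTP". TTP therefore inherits the methods of SAP Section 9.5.1, where "The distribution of PFS time including median and quartiles will be summarized descriptively using the Kaplan-Meier method" and where landmark rates, a stratified log-rank test and a stratified Cox hazard ratio are also planned.

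For TTNT, the event time runs "from randomization to the initiation of subsequent non-protocol anti-cancer treatment for multiple myeloma" (SAP Section 5, Time to Next Treatment). Under Section 9.5.2 a subject who starts no such therapy "will be censored at the date when the subject's information is last available", and "Time to next treatment will be summarized descriptively using the Kaplan-Meier method". Death is not mentioned, so a subject who dies untreated is censored by implication. No test or hazard ratio is specified for TTNT.

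The readable text gives no cumulative incidence or other competing-risk estimate for either endpoint. PFS and duration of response both count death as an event. TTP and TTNT are additional secondary endpoints, and their objective is a comparison between arms (Protocol Section 1.2; SAP Section 2.1). They lie outside the testing sequence of PFS, ORR, MRD[-]CR and OS (SAP Section 7.2).

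**The concern.** Kaplan-Meier treats a censored subject as someone who would go on to have the event at the same rate as those still under observation. That is reasonable for a subject cut off by the analysis date. It is not reasonable for a subject who has died, who can no longer progress or start new therapy. Once such deaths occur, 1 − KM is no longer the proportion who have progressed or started therapy, and the KM median is earlier than the time by which half of the subjects have done so.

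What is at stake is the descriptive reading of two listed secondary endpoints. The matter is sharper for TTNT: KM is its only specified summary, so no unaffected estimate stands beside it. For TTP the hazard ratio and log-rank test are unaffected, because they address the cause-specific hazard of progression.

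**Working it through.** **The plan's own figures.** The documents give no figure for TTP or TTNT. The design figures were checked first, because the illustration borrows its hazard ratio from them. The plan says "One hundred eighty-eight PFS events are required to have at least 90% power to demonstrate superiority at an alternative HR of 0.6", "using a log rank test at 1-sided overall significance level of 0.025". With 2:1 allocation the information is 188 × 2/9 = 41.78, whose square root is 6.464.
- Power = Φ(6.464 × |ln 0.6| − 1.960) = Φ(1.342) = 0.910, consistent with at least 90%.
- Minimum detectable hazard ratio = exp(−1.960/6.464) = 0.738, as stated.

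**Inputs for the illustration.**
- Kd median PFS of 18.7 months, from the earlier phase 3 Kd trial in Protocol Table 1 and Section 2.5.4. The readable text does not show this trial's own planning median.
- Hazard ratio 0.6 (SAP Section 3.2).
- Accrual over 11 months (Protocol Section 3.5.1) and primary analysis at 27 months (Protocol Section 3.5.2).
- Assumed, not in the documents: exponential times, and the share f of first events that are deaths without progression, varied from 5 to 20%.

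The Kd PFS hazard is h = ln 2/18.7 = 0.03707 per month.

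**Formulas.** Let λp be the hazard of progression and λd the hazard of death without progression.
- With deaths censored: 1 − KM(t) = 1 − exp(−λp t).
- Cumulative incidence: CIF(t) = λp/(λp + λd) × [1 − exp(−(λp + λd)t)].
- In Kd, λp = (1 − f)h and λd = fh.

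**Within-arm excess, Kd.** At f = 20% and month 24, 1 − KM = 1 − exp(−0.8 × 0.03707 × 24) = 50.9%. CIF = 0.8 × [1 − exp(−0.03707 × 24)] = 47.1%. The excess is 3.8 points. Across the range:

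| Death share f | Month 24: 1 − KM / CIF (%) | Excess | Month 48: 1 − KM / CIF (%) | Excess | Median, KM / CIF (months) |
|---|---|---|---|---|---|
| 5% | 57.1 / 56.0 | 1.1 | 81.6 / 79.0 | 2.6 | 19.7 / 20.2 |
| 10% | 55.1 / 53.0 | 2.1 | 79.8 / 74.8 | 5.0 | 20.8 / 21.9 |
| 15% | 53.1 / 50.1 | 3.0 | 78.0 / 70.7 | 7.3 | 22.0 / 23.9 |
| 20% | 50.9 / 47.1 | 3.8 | 75.9 / 66.5 | 9.4 | 23.4 / 26.5 |

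In simulation with 150 Kd subjects, the month-24 excess is 0.22 to 0.76 standard errors at the 27-month cutoff. The month-48 excess is 0.8 to 2.4 standard errors at a 59-month cutoff.

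**Between-arm gap.** Take f = 15% in Kd and month 48. In KdD, set λp to 0.6 times the Kd value and vary the KdD:Kd ratio of λd. By KM the two arms are 78.0% and 59.6%, a gap of 18.3 points whatever that ratio is. By cumulative incidence:

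| KdD:Kd hazard ratio for death without progression | CIF Kd / KdD (%) | CIF gap | KM gap minus CIF gap |
|---|---|---|---|
| 0.6 (same death share in both arms) | 70.7 / 55.8 | 14.9 | +3.4 |
| 1 | 70.7 / 53.4 | 17.3 | +1.0 |
| 1.5 | 70.7 / 50.6 | 20.0 | −1.7 |
| 2 | 70.7 / 48.1 | 22.6 | −4.3 |

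The sign changes within this range. Medians can point the opposite way from the curves. In the first row the KM medians are 22.0 and 36.7 months (difference 14.7), and the CIF medians are 23.9 and 39.9 months (difference 16.0).

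All of this models TTP. For TTNT the same algebra applies, but deaths after progression and before new therapy also compete. Those were not quantified.

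**The case against.** The strongest reply has four parts.

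1. TTP is openly defined. The SAP says that death is censored and nowhere calls 1 − KM the proportion who progress. This stands as a defence of the definition and of the Cox model. It does not help a reader who takes a KM median or landmark rate at face value.

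2. Nothing confirmatory depends on either endpoint. This stands in full. Death counts as an event in PFS and OS, and deaths are tabulated separately under SAP Section 9.6.2.

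3. The effect is small when the trial first reports. This stands for Kd, at under one standard error. The larger figures need a month-48 estimate from later follow-up, and no readable text fixes such a landmark. The SAP's scope does, however, extend to interim and final OS analyses, when longer follow-up will exist.

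4. Replacing KM would be a matter of taste and would hinder comparison with published KM estimates of TTP. This stands against replacement. It does not stand against adding a second estimate.

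**Conclusion.** The concern holds as a within-arm bias in description. Wherever deaths occur before the event, 1 − KM is too high and the KM median too early. For Kd TTP the excess is 1.1 to 3.8 points at month 24 and 2.6 to 9.4 points at month 48. These sizes rest on exponential times, a borrowed control median and an assumed 5 to 20% death share. The direction within each arm does not depend on those assumptions. The TTP log-rank test and Cox hazard ratio remain valid for the cause-specific hazard, and no alpha-controlled conclusion is touched.

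A reader might infer that the practice inflates the apparent benefit of KdD, since Kd has the higher event rate. The documents do not support that. The inference requires a hazard of death without progression that is equal in the arms or lower in KdD. Assuming the same death share in both arms builds in a 40% lower hazard in KdD. The documents give no arm-specific rates of such deaths. With a hazard 1.5 to 2 times higher in KdD, KM understates the gap at month 48, and even with equal shares it understates the difference in medians. The supportable statement is that the gap may be distorted in either direction.

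This is a cheap improvement to make, not a flaw that threatens the trial's conclusions.

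**What to change.** In SAP Section 9.5.2:
- Add Aalen-Johansen cumulative incidence estimates for TTP (competing event: death before progression) and for TTNT (competing event: death before new therapy).
- Report the cumulative incidence of the competing deaths by arm, so that a reader can judge which way the between-arm gap is distorted.
- State explicitly how death is handled for TTNT.
- Label the TTP log-rank test and hazard ratio as cause-specific.
- Keep the KM curves alongside for comparison with published figures.
- In the same edit, correct the TTP cross-reference to Section 8.4.1.1, which does not exist in this SAP. The PFS methods are in Section 9.5.1.

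No new data are needed: survival and subsequent therapy are already collected (Protocol Sections 7.3.13 and 7.3.14). The cost is a few lines of SAP text and a standard procedure. The downside is one extra display per endpoint.

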9.6 Safety Analyses

9.6.1 Analyses of Primary Safety Endpoint(s)

Safety and tolerability will be assessed, where applicable, by incidence, severity, seriousness, and changes from baseline for all relevant parameters including AEs, deaths, laboratory tests, and vital signs.

All safety analyses will be based on the Safety Analysis Set (see [section 6.2](#)).

9.6.2 Adverse Events

The Medical Dictionary for Regulatory Activities (MedDRA) version 20.0 or later will be used to code all events categorized as adverse events to a system organ class and a preferred term.

The subject incidence of adverse events will be summarized for all treatment-emergent adverse events, grade 3 or higher TEAEs, serious adverse events, adverse events leading to withdrawal of investigational product, and fatal adverse events, and adverse events of interest (EOI). In the event that a subject experiences repeated episodes of the same AE, the subject will be counted once within each system organ class and similarly

counted once within each preferred term and the event with the highest severity grade and/or strongest causal relationship to each treatment will be used for purposes of incidence tabulations.

Subject incidence of all treatment-emergent adverse events, grade 3 or higher TEAEs, serious adverse events, adverse events leading to withdrawal of investigational product, and fatal adverse events will be tabulated by system organ class **in alphabetical order** and preferred term in **descending frequency order**.

Subject incidence of events of interest (standardized MedDRA queries and/or Amgen customized queries) will also be summarized according to their categories and preferred term in descending order of frequency. Time to onset and duration of select EOs may also be summarized.

In addition, summaries of treatment-emergent AEs, grade 3 or higher TEAEs, serious adverse events, adverse events leading to withdrawal of investigational product, and fatal adverse events by preferred term in any treatment arm will be provided in descending order of frequency.

Summaries of treatment-emergent and serious adverse events will be tabulated by system organ class, preferred term, and grade. The fatal adverse events **will also be provided** by system organ class **in alphabetical order** and preferred term in descending order of frequency.

A summary of the number of deaths and the cause of death, classified by deaths within 30 days of last dose of study drug and deaths more than 30 days after the last dose, will be provided.

All AEs, including TEAEs, will be included in individual subject listings.

All on study deaths will be listed.

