10.2 Sample Size Considerations

One hundred eighty-eight PFS events are required to have at least 90% power to demonstrate superiority at an alternative HR of 0.6 (arm 1 vs arm 2), using a log rank test at 1-sided overall significance level of 0.025. [REDACTED]

[REDACTED] With 450 subjects randomized (300 in arm 1 vs 150 in arm 2), it is anticipated that 188 events will be accrued at approximately 27 months after the first subject is randomized assuming events follow an exponential distribution. [REDACTED]

[REDACTED] The description of sample size calculation for log-rank test factoring in accrual and dropout can be found in Lachin and Foulkes, 1986; Lakatos, 1988; and Chow et al, 2003. The actual timing of primary analysis will be determined by actual enrollment rate, dropout rate, and PFS event rate; hence, it is subject to change as these factors may vary in the study. The minimum detectable PFS HR is approximately 0.738 (corresponding to about 36% improvement in PFS) at the primary analysis. Amgen may choose to increase sample size upon observation of slower than expected PFS event rate.

[REDACTED] It is based

on safety and survival follow-up as described in Section 3.5.2. It is not directly linked to sample size calculation based on the primary endpoint of PFS outlined in this section.

The sample size calculation was performed using East[®] software (Version 6.3 or above).

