2.1 Objectives and Endpoints

Objectives	Endpoints
Primary	

 To compare carfilzomib, dexamethasone, and daratumumab (KdD) to carfilzomib and dexamethasone (Kd) in terms of progression free survival (PFS) in patients with multiple myeloma who have relapsed after 1 to 3 prior therapies 	
 Progression free survival defined as time from randomization until disease progression or death from any cause. Disease progression is determined by a blinded Independent Review Committee (IRC).
Secondary	

Key secondary objectives:
 
 To compare the overall response rate (ORR; defined as the proportion of best overall response of stringent complete response [sCR], complete response [CR], very good partial response [VGPR], and partial response [PR]) between two arms To compare the rate of minimal residual disease negative-complete response (MRD[-]CR) in bone marrow aspirates at 12 months (\pm 4 weeks) as determined by Next-Generation sequencing (NGS) between two arms To compare the overall survival (OS) between two arms 
Additional secondary objectives are to compare the following between the 2 arms:
 
 safety and tolerability duration of response (DOR) time to next treatment (TTNT) time to progression (TTP) 	
Key secondary endpoints:
 
 ORR, defined as the proportion of subjects with best overall response (BOR) of stringent complete response (sCR), complete response (CR), very good partial response (VGPR), and partial response (PR) by IRC MRD[-]CR rate, defined as proportion of subjects with BOR of CR or better by IRC per International Myeloma Working Group Uniform Response Criteria (IMWG URC) and MRD[-] status as assessed by NGS (at a 10^{-5} level) at 12 months OS, defined as time from randomization until death from any cause. 
Additional secondary endpoints:
 
 DOR, defined as the time from first evidence of PR or better per IMWG-URC to the earliest of disease progression or death due to any cause for subjects with a best response of PR or better

Objectives	Endpoints

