9.6.7 Exposure to Investigational Product

Drug exposure (for carfilzomib, dexamethasone, daratumumab, respectively) including duration and intensity will be summarized descriptively for each treatment group.

Descriptive statistics will be produced to describe the exposure to investigational product by treatment group. The number of cycles of protocol-specified therapy administered will be summarized with an additional breakdown of the number of cycles started. In addition, the duration of therapy, the cumulative dose, and the average dose per administration and relative dose intensity will be summarized for each drug. The number and percent of subjects with dose modifications (eg, dose reductions, dose interruptions) and reason for modification will be summarized for both treatment groups.

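### Adverse events are compared by crude subject incidence, so if KdD subjects stay on treatment longer, equal event rates can look like excess toxicity

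*SAP*

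**What the plan says.** On safety, SAP 2.1 lists safety and tolerability first under this lead-in: "Additional secondary objectives are to compare the following between the 2 arms". The method in SAP 9.6.2 is: "The subject incidence of adverse events will be summarized for all treatment-emergent adverse events". Each subject counts once per system organ class and once per preferred term. Protocol 10.4.4 likewise plans numbers and percentages of subjects.

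SAP section 5 counts an event as treatment-emergent from the first dose until 30 days after the last dose of any study treatment, or the end of study if earlier. SAP 3.1 continues treatment to progression, unacceptable toxicity, withdrawal, death or 4 years. Under Protocol 6.2.1.2 and 6.2.2.2 a subject remains on treatment while taking either carfilzomib or daratumumab.

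Exposure has its own section, SAP 9.6.7: "Drug exposure (for carfilzomib, dexamethasone, daratumumab, respectively) including duration and intensity will be summarized descriptively for each treatment group". Nothing visible links it to the event tables. The one time-related provision for adverse events is in 9.6.2: time to onset and duration may be summarized for selected events of interest.

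On design, SAP 3.2 states: "One hundred eighty-eight PFS events are required to have at least 90% power to demonstrate superiority at an alternative HR of 0.6".

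**The concern.** The proportion of subjects with at least one event rises with time at risk. The window lengthens with time on treatment, and the trial is designed around a regimen that delays the main reason for stopping. If that hypothesis is right, KdD subjects are likely to be observed longer for adverse events, and the crude percentage would be higher in KdD even where the monthly event rate is identical.

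What is at stake is the reading of a stated comparison objective: part of a difference of a few percentage points could be attributed to adding daratumumab when it reflects longer observation. The distortion also grows with follow-up, so safety tables updated at later analyses would be more affected than those at the primary analysis.

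**Working it through.** **1. The plan's own figures.** Inputs from SAP 3.2: 188 events, HR 0.6, 2:1 allocation, one-sided 0.025.

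- Information: 188 × (2/3) × (1/3) = 41.8, square root 6.464.
- Power: Φ(6.464 × 0.5108 − 1.96) = Φ(1.342) = 0.910, which meets the stated minimum of 90%.
- Smallest significant HR: exp(−1.96/6.464) = 0.738, matching "The minimum detectable PFS HR that will achieve statistical significance is approximately 0.738".
- Timing: Protocol 10.2 says "it is anticipated that 188 events will be accrued at approximately 27 months after the first subject is randomized". With uniform accrual over 11 months (Protocol 3.5.1), exponential PFS and a Kd median of 18.7 months, 195 events are expected by month 27 without dropout and 186 with 0.5% dropout per month. The assumed median is therefore consistent with the plan.

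**2. Assumptions for the exposure step.**

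- Kd median PFS 18.7 months, from the earlier phase 3 trial described in Protocol 2.5.4, because the design value is blacked out. Progression-or-death hazards: ln 2/18.7 = 0.0371 per month in Kd and 0.6 × 0.0371 = 0.0222 in KdD.
- Event hazard a, equal in both arms. The documents give none; 0.02 per month is illustrative.
- Cutoffs at months 27 and 59. Month 59 is constructed as 11 months of accrual plus the 48-month maximum in SAP 3.1.
- Stopping for other reasons: either none, or an equal hazard in both arms that brings the Kd treatment median to 48 weeks (11.04 months), the carfilzomib duration quoted in Protocol 2.5.4. That hazard is ln 2/11.04 − 0.0371 = 0.0257 per month.
- The 30-day tail is left out. It adds at most about one month per subject in each arm.

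**3. Formulas.** For total stopping hazard h and available follow-up t (capped at 48 months), averaged over entry times:

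- mean exposure = (1 − exp(−ht))/h
- crude incidence = a/(a + h) × (1 − exp(−(a + h)t))

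**4. Results at a = 0.02 per month.**

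| Cutoff | Stopping | Mean exposure, KdD vs Kd (months) | Crude incidence, KdD vs Kd | Ratio |
|---|---|---|---|---|
| 27 | Progression or death only | 17.0 vs 14.7 | 28.1% vs 24.6% | 1.14 |
| 27 | Kd median 48 weeks, equal other stopping | 13.3 vs 11.7 | 22.4% vs 19.9% | 1.13 |
| 59 | Progression or death only | 29.5 vs 22.4 | 41.1% vs 32.8% | 1.25 |
| 59 | Kd median 48 weeks, equal other stopping | 18.8 vs 15.1 | 28.3% vs 23.7% | 1.19 |

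For event hazards from 0.002 to 0.15 per month, the ratio runs from 1.07 to 1.15 at month 27 and from 1.08 to 1.31 at month 59. First events per patient-time at risk give 0.02 per month, or 24 per 100 patient-years, in both arms: a ratio of 1.00.

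**5. Falling event rates.** Protocol 2.5.4 reports yearly Kd percentages of 74.1, 52.8, 44.9 and 29.0 for grade 3 events, and 47.9, 32.5, 24.7 and 3.2 for serious events. Treat each as a within-year first-event risk (an assumption), convert it to a monthly hazard by −ln(1 − p)/12, and use it in both arms. Across both cutoffs and both stopping models:

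- grade 3: ratio 1.08 to 1.11
- serious: ratio 1.10 to 1.14
- either set of hazards divided by ten, to mimic rarer single terms: 1.11 to 1.20

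**6. Where the effect is absent.** For events confined to the first month, incidence is 4.8% vs 4.8% at a hazard of 0.05 and 17.9% vs 17.8% at 0.2. In the 48-week model, total stopping is equal in the two arms when the KdD hazard for other reasons is (0.0257 + 0.4 × 0.0371)/0.0257 = 1.58 times that of Kd. Above this the bias reverses.

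**The case against.** Four points on the other side carry weight.

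- **Direction is inferred.** The documents assume a PFS benefit; they do not forecast treatment duration. A triplet could be stopped more often for toxicity. A reader might infer that KdD will necessarily show spurious excess toxicity. The documents do not support that: with non-progression stopping about 1.6 times as frequent in KdD, the effect is gone. This stands, and limits the claim to what can happen.
- **Larger ratios are not supported.** A reader might apply HR 0.6 to every reason for stopping, with a 48-week Kd median, and obtain 1.23 at month 27 and 1.37 at month 59. The plan gives 0.6 for PFS only. Equal stopping for other reasons gives 1.13 and 1.19, below the progression-only figures.
- **Crude incidence is not the only safety summary.** A reader might infer that nothing else compares the arms. In fact, vital signs, ECG, echocardiography and pulmonary function (SAP 9.6.4, 9.6.5, 9.7.4, 9.7.5) are summarized by visit or over time. Deaths are split at 30 days after last dose, and survival is analysed by Kaplan-Meier and Cox methods. The gap concerns adverse events.
- **The tables are descriptive.** No test or error rate depends on them, exposure is reported by arm, and the crude percentage is a valid estimate of the risk of an event while on each regimen.

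The last point lowers the severity but does not close the gap. A reader who sees longer exposure in one table and higher incidence in another cannot separate the two without patient-time at risk for each event.

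**Conclusion.** The point holds as a cheap improvement, not as an error that invalidates the plan. Adverse events are compared by a measure that depends on time at risk, in a design where time at risk is likely to differ if the primary hypothesis is true.

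The distortion is moderate. Under equal event hazards of 0.02 per month it is about 13% to 14% relative at the primary analysis (2.5 to 3.5 percentage points) and about 19% to 25% with full follow-up (4.6 to 8.3 points). It is smaller, about 8% to 14%, if event rates fall as in the protocol's background, and up to about 20% for rarer events.

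These sizes rest on the 18.7-month median, the illustrative event hazard, the constructed month-59 cutoff and the 4-year cap. The direction rests on non-progression stopping not being much more frequent in KdD. Events concentrated at the start of treatment, such as infusion reactions, are barely affected.

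**What to change.** In SAP 9.6.2, keep the crude tables and prespecify two additions for grade 3 or higher, serious and of-interest events:

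- exposure-adjusted rates by arm, as first events per 100 patient-years at risk, with the rate difference and its 95% CI; time at risk ends at the first event or at the close of the treatment-emergent window
- subject incidence by 12-month interval of exposure, among subjects still at risk at the start of each interval

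Fatal events need no separate rate, since the overall survival analysis already compares mortality over time.

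The cost is a few descriptive tables from dates already collected; no endpoint, test or alpha changes. The downside is that a single overall rate assumes a constant hazard, which the protocol's background figures contradict. The interval version covers that. Prespecification matters because the trial is open-label, and adjusted rates added after the data are seen could look selective.
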